### 3.3 Risk/Benefit Assessment

#### 3.3.1 Known Potential Risks

The safety of Qelbree has been evaluated in 189 adult participants (18 to 60 years of age) with ADHD exposed to one or more doses ranging from 200 mg to 600 mg QD in a short-term (6 week), randomized, double-blind, placebo-controlled trial (Study 812P306). Approximately 9% of the 189 participants receiving Qelbree discontinued treatment due to an adverse reaction. The adverse reactions most commonly associated with discontinuation of Qelbree were fatigue (n=4), insomnia (n=3), constipation (n=3), and headache (n=2). The most commonly reported adverse reactions (occurring at  $\geq 5\%$  and at least twice the placebo rate of Qelbree) were insomnia, headache, somnolence, fatigue, nausea, decreased appetite, dry mouth, and constipation ([Qelbree PI](#)).

Adverse Events of concern include ([Qelbree PI](#)):

- Suicidal Thoughts and Behavior: Among 189 adults treated with Qelbree, a total of three participants (1.6%) reported suicidal ideation on the C-SSRS, versus 0 of 183 adults treated with placebo. No adults treated with either Qelbree or placebo reported suicidal behavior on the C-SSRS in the study. No attempted or completed suicides occurred in the trial. Participants treated with Qelbree had higher rates of insomnia and irritability. Although a causal link between the emergence of insomnia and irritability and the emergence of suicidal impulses has not been established, there is a concern that these and other symptoms such as depressed mood, anxiety, agitation, akathisia, mania, hypomania, panic attacks, impulsive behavior, and aggression may represent precursors to emerging suicidal ideation or behavior.
- Blood Pressure and Heart Rate Increases: In a clinical study in adult participants (18 to 60 years of age), 52/178 (29%) of participants treated daily with Qelbree (200 mg to 600 mg) had a  $>20$  beat per minute (bpm) increase in pulse rate at any time point in the clinical trial, compared to 23/181 (13%) of participants who received placebo. Of participants treated daily with Qelbree (200 to 600 mg), 23/178 (13%) had a  $\geq 15$  mmHg increase in diastolic blood pressure at any time in the clinical trial, compared to 16/181 (9%) of participants in the placebo group.

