4.3. Exploratory Efficacy Variables

5. STATISTICAL CONSIDERATIONS

5.1. General Statistical Methods

All statistical analysis will be performed using SAS version 9.4 or higher. All statistical analyses will be presented using descriptive statistics. Summary statistics for continuous variables will include sample size (N), mean, median, standard deviation, interquartile range (Q1 and Q3), minimum, and maximum. Standard error may be added if it is needed for the display and interpretation of some efficacy results. Summary statistics for categorical variables will be presented in terms of frequencies and percentages. Participant data listing to support summaries will be provided.

Unscheduled measurements (unless defined as baseline or otherwise specified) will be excluded from descriptive statistics performed by visits in summary tables but will be included in data listings and other analyses that not performed by visit. For assessments that are repeated, unless otherwise specified, the non-missing values from the first assessment will be used for generating summary statistics.

Mean (\pm SE) profiles and Mean (\pm SE) CFB for AISRS total score, MADRS, HAM-A and GAD-7 will be plotted by visit.

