5.2. Baseline Definitions

Baseline is defined as the last non-missing assessment measured prior to the start of SM.

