8.2.2. Shift in Vital Signs

Compared to the reference range, each of the three vital signs variables (diastolic blood pressure, systolic blood pressure and pulse rate) values will be classified as low, normal, high or missing. Shift tables for the change from baseline to all study visits will be summarized using number and percentage of subjects by visit.

Vital sign normal ranges are presented in [Table 1](#).

Table 1. Vital Signs Normal Ranges

Parameter	Low	High
Diastolic blood pressure (mmHg)	60	90
Systolic blood pressure (mmHg)	90	140
Pulse rate	50	100

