8.3. Columbia Suicide Severity Rating Scales (C-SSRS)

The number and percentage of subjects with a response of “Yes” by categories for suicidal ideation, suicidal behavior and suicidal ideation or behavior will be summarized descriptively by visit. The listing for C-SSRS will be provided.

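### The C-SSRS and vital-sign tables are all by visit, so the plan gives no per-participant, any-time count of suicidality or of marked pulse and diastolic pressure rises

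*SAP*

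**What the plan says.** **C-SSRS.** SAP 8.3 counts participants answering yes by category, and the results for "suicidal ideation, suicidal behavior and suicidal ideation or behavior will be summarized descriptively by visit". It adds: "The listing for C-SSRS will be provided". No overall or any-time row is mentioned. Protocol 12.9 plans C-SSRS numbers and percentages by category and does not limit them to by visit. SAP 9 declares no changes from the protocol's analyses.

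**Vital signs.** SAP 8.2.1 summarizes observed values and changes by visit. SAP 8.2.2 says: "Shift tables for the change from baseline to all study visits will be summarized using number and percentage of subjects by visit". The limits are fixed: pulse 50 to 100, diastolic pressure 60 to 90 mmHg, systolic pressure 90 to 140 mmHg. Protocol 12.9 also asks for vital signs by study visit, so here the SAP follows the protocol.

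**Unscheduled values.** SAP 5.1 opens its rule with "Unscheduled measurements (unless defined as baseline or otherwise specified") and says that such values "will be excluded from descriptive statistics performed by visits in summary tables". It keeps them in the listings and in any analysis that is not broken down by visit. SAP 8.2 and 8.3 specify nothing different. SAP 5.7 uses nominal visits without windows and maps early-termination visits to the next scheduled visit.

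**How the known risks are stated.** Protocol 3.3.1 reports C-SSRS ideation per participant. It also counts participants with a greater than 20 "beat per minute (bpm) increase in pulse rate at any time point in the clinical trial", and gives the matching count for diastolic rises of 15 mmHg or more.

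**The concern.** Protocol section 4 says the safety endpoints were chosen to address the cautions and warnings in the prescribing information. Suicidality and rises in pulse and blood pressure are among the adverse events of concern that the protocol names. Participants must have a MADRS or HAM-A total above 22. The natural safety result is the share of participants who had such a finding at any time on treatment, and the planned tables do not give it.

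The gap exists even if no unscheduled measurement is ever taken, because three by-visit percentages do not determine an any-time incidence. Unscheduled measurements add to it: a positive result found at one would be listed, but would enter no C-SSRS or vital-sign table.

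**Working it through.** The plan states no figure of its own on this point. The check is a reading of the rules, with arithmetic for scale.

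**1. Which tables can hold an unscheduled value?** SAP 8.2.1, 8.2.2 and 8.3 are all by visit, and SAP 5.1 excludes unscheduled values from by-visit tables. SAP 5.7 applies no windows, so such a value is not moved into a neighbouring visit. It goes to the listings. Early-termination values are tabulated through the mapping in SAP 5.7.

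**2. Can an any-time count be recovered from by-visit counts?** Let k4, k9 and k14 be the numbers positive at the three post-baseline visits, and A the number positive at any of them. Then max(k4, k9, k14) ≤ A ≤ k4 + k9 + k14. For example, 12 positive responses spread equally (4 per visit) could come from as few as 4 participants or as many as 12. The by-visit denominators also shrink, since 33% attrition is expected.

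**3. Does the shift table show the rises that the protocol counts?** Not necessarily.
- Pulse: the smallest whole-number rise above 20 bpm is 21. A baseline of 50 to 79 becomes 71 to 100, which does not exceed the upper limit of 100.
- Diastolic pressure: a rise of 15 mmHg takes a baseline of 60 to 75 to 75 to 90, which does not exceed 90.

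Such participants can be classed normal to normal. The change summaries in SAP 8.2.1 include the mean, quartiles and maximum, so a large rise would show in the maximum. They do not give the number of participants above a threshold.

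**4. Scale.** The percentages in protocol 3.3.1 reproduce: 3/189 = 1.6%, 52/178 = 29.2%, 23/178 = 12.9%. Applied to 750 dosed participants:
- ideation: 750 × 3/189 = 11.9, about 12
- pulse rise: 750 × 52/178 = 219.1, about 219
- diastolic rise: 750 × 23/178 = 96.9, about 97

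The documents do not say what share would be seen only at an unscheduled contact. For an assumed 5% to 50%:
- ideation: 11.9 × 0.05 = 0.6 to 11.9 × 0.50 = 6.0
- pulse rise: 219.1 × 0.05 = 11 to 219.1 × 0.50 = 110

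The range is illustrative. The true share may lie at or below its lower end.

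**The case against.** **No unscheduled assessment is planned.** The schedule of events places C-SSRS and blood pressure/pulse only at screening and Weeks 4, 9 and 14. This stands. The number of affected records is unknown, and the case for change rests mainly on the missing any-time count.

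**Adverse event tables give partial cover.** Protocol 9.4.1 has adverse events captured at every contact, protocol 9.5.5 names suicidality and pulse/pressure rises as events of concern, and the tables in SAP 8.1 count each participant once over the whole study. A reader might infer that an unscheduled positive result reaches no summary table at all. That is too strong, because it is counted if recorded as an adverse event. The cover is only partial, since no rule requires a positive C-SSRS or a pulse rise to be so recorded.

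**The next form may capture the event.** A reader might infer that a later *Since Last Visit* form would not repeat an interval event. The documents do not give the instrument's rules, and the version's name suggests that it could. A participant lost to follow-up is not expected to complete the Week 14 procedures (protocol 10.2), so may have no later form.

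**Baseline.** SAP 5.2 says: "Baseline is defined as the last non-missing assessment measured prior to the start of SM". A reader might infer that ideation reported at Televisit 1a is thereby discarded in favour of the 1b form. SAP 8.3 has no baseline-relative C-SSRS analysis, so nothing planned is distorted. The rule would matter only if a new-onset analysis were added.

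**Comparison with Study 812P306 is not an objective.** This is correct. That trial was controlled, lasted 6 weeks and excluded depression and anxiety. This one is uncontrolled, lasts 14 weeks and relies on self-reported readings. Any comparison would be descriptive.

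**Conclusion.** The point holds as a gap in reporting. As written, the plan cannot state how many participants had suicidal ideation or behavior, or a marked pulse or diastolic rise, at any time on treatment. For C-SSRS, the SAP is also narrower than protocol 12.9. The data are not lost: they are listed, early-termination values are tabulated, and adverse event tables may count some of the events.

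The figures of about 12, 219 and 97 participants assume that the earlier trial's rates carry over, which its different length and population make uncertain. They show only that the missing counts are unlikely to be trivial. The documents do not support saying that many of the rises would stay inside the fixed limits. They show that this can happen, but not how often.

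**What to change.** - **SAP 8.3:** add an any-time post-baseline table with the number and percentage of participants in each C-SSRS category, using all post-baseline records including unscheduled ones. Split it into new-onset or worsened against the worst pre-dose response across Televisits 1a and 1b. State that reference explicitly, because the general baseline rule would otherwise take only the last pre-dose form. The split is useful because exclusion criterion 6 names ideation items 4 and 5, so lower-level ideation at entry is not in itself excluded.
- **SAP 8.2:** add any-time post-baseline counts of participants with a pulse increase above 20 bpm and with a diastolic increase of at least 15 mmHg. These are the reporting thresholds already in protocol 3.3.1.

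No exemption from the unscheduled-value rule is needed, because SAP 5.1 already admits such values to analyses not done by visit. Early-termination values need no new rule either. Saying that all post-baseline records count also settles SAP 5.1's separate default of using the first of any repeated assessments.

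The cost is two tables from data already collected. Reported rates may be higher than the by-visit figures, and any comparison with Study 812P306 should be labelled descriptive.

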9. CHANGES FROM THE PROTOCOL

There are no changes from the planned analyses in the study protocol.

11. APPENDICES

Table 2. Schedule of Procedures and Assessments

Study Period	Screening Period			Treatment Period			EOS ¹⁰	SF
Week of Study	—	—	—	—	4	9	14	15
Televisit ¹ No.	1a	1b	—	—	2	3	4	5
Day of Study	- 28 to -1		- 7 to -1	1	29	64	99	106
Window (days)	—	—	—	—	± 3	± 3	± 3	± 3
Informed Consent	X							
Schedule Next Televisit	X	X			X	X	X	
Review Inclusion/Exclusion Criteria	X	X						
Demographics	X							
Medical/Psychiatric/Social History	X							
RMCH Questionnaire	X ²	X ²			X ³	X ³	X ³	
Review Prior Medications ⁴	X							
Review Concomitant Medications	X	X			X	X	X	X
Review Adverse Events					X	X	X	X
Ship BP/PR cuff ⁵	X							
Ship UPT (FOCP only) ⁵	X							
Confirm Negative UPT (FOCP only)	X				X	X	X	
BP/PR and Weight ^{5,6}	X				X	X	X	
Height ⁷	X							
MINI-AS (DSM-5-TR)	X							
AISRS (ClinRO)		X			X	X	X	
CGI-S (ClinRO)		X			X	X	X	
CGI-C (ClinRO)					X	X	X	
SIGMA (ClinRO)		X					X	
SIGH-A (ClinRO)		X					X	
C-SSRS (Baseline/Screening version)	X							
C-SSRS (Since Last Visit version)		X			X	X	X	
Mobile App Training Module (PROs)		X						
Dispense SM			X		X	X		
First Dose of Qelbree ⁸				X				
ASRSv1.1-SC (PRO) ⁹		X			X	X	X	
PHQ-8 (PRO) ⁹		X			X	X	X	

Study Period	Screening Period			Treatment Period			EOS ¹⁰	SF
Week of Study	—	—	—	—	4	9	14	15
Televisit ¹ No.	1a	1b	—	—	2	3	4	5
Day of Study	- 28 to -1		- 7 to -1	1	29	64	99	106
Window (days)	—	—	—	—	± 3	± 3	± 3	± 3
GAD-7 (PRO) ⁹		X			X	X	X	
WPAI:SHP (PRO) ⁹		X			X	X	X	
PSQI (PRO) ⁹		X					X	
BRIEF-A (PRO) ⁹		X					X	
SM Administration Mode/Time ⁹					X	X	X	
SM Accountability					X	X	X	
Participant Ship/Return Unused SM ¹⁰							X	

Abbreviations: AISRS = Adult ADHD Investigator Symptom Rating Scale; ASRSv1.1-SC = Adult ADHD Self-Report Scale Version 1.1 Symptom Checklist; BRIEF-A = Behavior Rating Inventory of Executive Function-Adult Version; BP = Blood Pressure (systolic/diastolic); CGI-S = Clinical Global Impression Scale of Severity; CGI-C = Clinical Global Impression Scale of Change; C-SSRS = Columbia Suicide Severity Rating Scale; ClinRO = Clinician-Reported Outcomes; EOS = end of study; FOCP = Females of Childbearing Potential; GAD-7 = General Anxiety Disorder-7 item; MINI-AS = Mini International Neuropsychiatric Interview for ADHD Studies; PHQ-8 = Patient Health Questionnaire 8-item; PRO = Patient-Reported Outcomes; PSQI = Pittsburgh Sleep Quality Index; PR = Pulse Rate; RMCH = Reproductive/Menstrual Cycle History; RMCH mQ5 = RMCH Questionnaire (Menstrual-Question #5); SF = Safety follow-up; SIGH-A = Structured Interview Guide for the Hamilton Anxiety Scale; SIGMA = Structured Interview Guide for the Montgomery and Åsberg Depression Rating Scale; SM = study medication; UPT = Urine Pregnancy Test; WPAI:SHP = Work Productivity and Activity Impairment:Specific Health Problem Questionnaire.

Footnotes:

1. Virtual televisits will last between 45 to 120 minutes. Consent will occur on or before Telehealth Visit 1a.
2. Administer full/entire RMCH Questionnaire (1 up to 8 items) to biological females at Screening only (if not administered at Televisit #1a, administer at Televisit #1b).
3. Only administer the RMCH mQ5 to FOCPs at Televisit #2, #3, and #4 during Treatment [Week 4, Week 9, and Week 14/EOS, respectively].
4. All medications (especially stimulant or non-stimulant ADHD medications) taken 12 months prior to Screening.
5. BP/PR cut (and UPT) will be shipped once participant is determined eligible. Prior to taking first dose, participant will measure and record BP/PR and weight (and confirm a negative UPT).
6. Weight will be collected with shoes off. BP/BR will be measured in a seated position. Self-reported by the participant to the study team on Day 1 and thereafter reported during scheduled televisits.
7. Height (with shoes off) will be self-reported to the study team.
8. Participant will need to report time, date, and dose of SM within the study mobile app on Day 1
9. PROs and questions about SM administration method and timing will be completed in the study mobile app.
10. At Week 14 the participant will be required to return all SM to Sponsor for destruction upon confirmation of proper SM accountability.
11. If participant discontinues early (Early-Termination), perform Week 14 assessments; however, ClinRO/PRO efficacy assessments should not be administered if participant has not taken daily dose of Qelbree for >7 consecutive days prior.
